## 12. DISEASE HISTORY

The following disease history characteristics will be summarized overall and by treatment group based on the SAF analysis population:

- Time since diagnosis (days) – calculated relative to date of first infusion of study drug
- Use of insulin pump (yes/no)
- HbA1c at diagnosis, screening, and baseline (%)
- Change and percent change in HbA1c from diagnosis to baseline (%)
- Weight at diagnosis, screening, and baseline (kg)
- Change and percent change in weight from diagnosis to baseline (kg)
- BMI at diagnosis, screening, and baseline (kg/m^2)

Author:	[name]	Version Number:	2.0
Template No.:	CS_TP_BS016 Revision 6	Version Date:	23Nov2022
Effective Date:	02Dec2019	Reference:	CS_WI_BS005

- Change and percent change in BMI from diagnosis to baseline (kg/m^2)

All disease history characteristics will be listed.

## 12.1. DERIVATIONS

‘Time since’ disease history characteristics, in days, will be calculated as follows:

- Time since diagnosis (days) = (Date of first infusion of study drug - Date of diagnosis)

Change from diagnosis will be calculated as follows:

- Change from diagnosis = Test value at screening or first dosing visit – Diagnosis value

Percent change from baseline will be calculated as:

- Percent change from diagnosis (%) = (Change from diagnosis at screening or fist dosing visit / diagnosis value)  
\* 100%

BMI, in kg/m^2, will be calculated as follows:

- BMI (kg/ m^2) = weight (kg)/ [height (m)]

## 13. MEDICATIONS

All medications will be coded using the World Health Organization (WHO) Drug Global dictionary, version B3 March 2020. Prior medications are defined as any medication that stopped before the date of first dose of study drug. Concomitant medications are defined as any medication that were ongoing or ended at the date of first dose of study drug, or any medication that started on or after the date of first dose of study drug.

Partially or completely missing medication start and stop dates will be handled as described in APPENDIX 1.

Prior and concomitant medications will be summarized separately by Anatomical Therapeutic Class (ATC) level 2 and preferred drug name by treatment arm and overall based on the safety analysis population. A subject having more than one medication within the same ATC Level 2 or preferred drug name will be counted only once for that ATC Level 2 or preferred drug name.

All medications (prior and concomitant) will be listed.

Author:	[name]	Version Number:	2.0
Template No.:	CS_TP_BS016 Revision 6	Version Date:	23Nov2022
Effective Date:	02Dec2019	Reference:	CS_WI_BS005

## 14. EXPOSURE TO STUDY DRUG

Exposure to the study drug will be summarized by treatment group based on the SAF analysis population for the following measures:

- Treatment duration, weeks
- Cumulative drug exposure, mL
- Total number of doses administered, n
- Dose intensity, %
- Any dose modification (dose held, interrupted, reduced, or permanently withdrawn)

### 14.1. DERIVATIONS

Measures of drug exposure will be calculated as follows:

- Treatment duration (weeks) = (Date of last injection of study drug – Date of first injection of study drug + 30.4167) / 7
- Cumulative drug exposure (mL) = the sum of “Volume Administered (mL)” recorded on the *Dose* eCRF page, across all study dosing days
- Total number of doses administered = count of records on the *Dose* eCRF page where the response to the question “Was IP/Placebo administered at this visit” is Yes.
- Dose intensity (%) = (Cumulative drug exposure (mL) / Total planned dose (mL))\*100, where total planned dose = (20 mL \* 3)

The dates of first and last AVT001 administration will be taken from the eCRF *Dose* page.

## 15. COMPLIANCE WITH STUDY DRUG

Because IP will be administered intravenously to the subjects enrolled in the study in accordance with the protocol, compliance will not be assessed.

Author:	[name]	Version Number:	2.0
Template No.:	CS_TP_BS016 Revision 6	Version Date:	23Nov2022
Effective Date:	02Dec2019	Reference:	CS_WI_BS005

## 16. EFFICACY ENDPOINTS

Unless otherwise indicated, all efficacy summaries and figures will be presented by treatment group and visit, when appropriate, based on the SAF analysis population.

### 16.1. PRIMARY EFFICACY

There are no primary efficacy endpoints in this study.

### 16.2. SECONDARY EFFICACY

The secondary efficacy endpoints analyzed in this SAP are:

- Change from baseline in the area under the curve (AUC) of the stimulated C-peptide levels over the first 4 hours of a mixed meal tolerance test (MMTT).
- Change from baseline in HbA1c.
- Change from baseline in total, basal, and bolus daily insulin dose.
- Changes from baseline in autoantibody levels.

#### 16.2.1. SECONDARY EFFICACY ENDPOINT VARIABLES AND DERIVATIONS

##### 16.2.1.1. Change from Baseline in the Area under the Curve (AUC) of the stimulated C-peptide levels over the first 4 hours of a mixed meal tolerance test (MMTT)

The area under the stimulated C-peptide curve (AUC) over the first 4-hour period of a mixed meal glucose tolerance test will be calculated using the trapezoidal rule that is a weighted sum of the C-peptide values over the 240 minutes. Missing C-peptide levels at any given timepoint will not be imputed. In the calculation of the AUC when C-peptide levels are missing, a line will be drawn from the last timepoint with a non-missing C-peptide to the next timepoint with non-missing C-peptide.

Change from baseline in C-peptide AUC will be computed for baseline and for each post-baseline visit where MMTT was a scheduled assessment.

Author:	[name]	Version Number:	2.0
Template No.:	CS_TP_BS016 Revision 6	Version Date:	23Nov2022
Effective Date:	02Dec2019	Reference:	CS_WI_BS005

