## 6.5. COMMON CALCULATIONS

Change from baseline will be calculated as:

- Change from baseline = Test value at post-baseline visit – Baseline value

Percent change from baseline will be calculated as:

- Percent change from baseline (%) = (Change from baseline at post-baseline visit / Baseline value) \* 100%

For select parameters where data is available, change and percent change will also be calculated from diagnosis.

Author:	[name]	Version Number:	1.0
Template No.:	CS_TP_BS016 Revision 6	Version Date:	28Mar2022
Effective Date:	02Dec2019	Reference:	CS_WI_BS005

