## **6.5. COMMON CALCULATIONS**

Change from baseline will be calculated as:

- Change from baseline = Test value at baseline or post-baseline visit – Baseline value

Percent change from baseline will be calculated as:

- Percent change from baseline (%) = (Change from baseline at baseline or post-baseline visit / Baseline value) \* 100%

For select parameters where data is available, change and percent change will also be calculated from diagnosis.

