#### **16.2.1.2. Change from Baseline in HbA1c**

HbA1c will be measured at the first screening visit and at each dosing and long-term follow-up visit as per the schedule of events (refer to protocol Table 3).

Change from baseline in HbA1c will be computed for baseline and for each post-baseline visit.

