- MMRM, based on the data locked for the primary analysis when the last subject completes the Month 5 study visit (Day 150), with the data at Visit 3/Day 1 included. A separate backward stepwise variable selection process will be performed.
- MMRM, based on the data locked for the primary analysis when the last subject completes the Month 5 study visit (Day 150), with the data at Visit 3/Day 1 excluded. A separate backward stepwise variable selection process will be performed.
- MMRM, based on the data locked for the supplemental analysis when the last subject completes the Month 12 study visit (Day 360), with the data at Visit 3/Day 1 excluded. A separate backward stepwise variable selection process will be performed.
- MMRM, based on the data locked for the supplemental analysis when the last subject completes the Month 12 study visit (Day 360), with the data at Visit 3/Day 1 excluded. The full model will be fitted directly without any variable selection process. The primary analysis performed in June 2022 for Day 150 reported results from the full model without any variable selection process, and with the data at Visit 3/Day 1 excluded.

Author:	[name]	Version Number:	2.0
		Version Date:	23Nov2022
Template No.:	CS_TP_BS016 Revision 6	Reference:	CS_WI_BS005
Effective Date:	02Dec2019		

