## **Summary of Change, SAP v2.0 vs SAP v1.0**

- **Added supplementary analysis for Day 360**
- **Defined Change from Baseline at baseline, so that the baseline data can be included in MMRM**
- **Defined the imputation rule for Potency Assay results on Day 1 (which was not planned to be collected on Day 1 per protocol), based on the Potency Assay results from Screening**
- **In addition to Total Daily Insulin usage, also added Total Daily Insulin usage divided by weight as a secondary endpoint**
- **Added additional MMRM analysis for C-peptide AUC, HbA1c, Total Daily Insulin usage, and 4 auto-antibodies.**

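### SAP v2.0 defines a Day 1 change from baseline that is always 0 so that it can enter the MMRM; where it enters, the planned covariance fit has no finite optimum and the fallback structures can give SEs that are too small

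*Combined protocol and SAP*

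**What the plan says.** SAP v1.0 section 6.5 defined "Change from baseline = Test value at post-baseline visit" minus the baseline value. SAP v2.0 section 6.5 widens the first term to "Test value at baseline or post-baseline visit". Section 16.2.1.1 applies this to C-peptide AUC: "Change from baseline in C-peptide AUC will be computed for baseline and for each post-baseline visit where MMTT was a scheduled assessment". Section 16.2.1.2 does the same for HbA1c ("Change from baseline in HbA1c will be computed for baseline and for each post-baseline visit"), and 16.2.1.3 and 16.2.1.4 for insulin and autoantibodies. The Summary of Change gives the reason: "so that the baseline data can be included in MMRM".

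The main C-peptide MMRM (16.2.2.1) has change from baseline as the outcome. It adjusts for baseline, age, time from diagnosis, HbA1c, BMI, insulin per weight and potency, each without a visit interaction, and uses REML, an unstructured (UN) covariance and Kenward-Roger. If a fit fails to converge, the next structure is tried: heterogeneous Toeplitz, heterogeneous AR(1), Toeplitz, AR(1). The text does not say which visits supply outcomes.

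Four exploratory C-peptide models follow. One Day 150 model is fitted "with the data at Visit 3/Day 1 included" and the other without Day 1. Both Day 360 models are on data locked "when the last subject completes the Month 12 study visit (Day 360), with the data at Visit 3/Day 1 excluded", one with variable selection and one as the full model. The June 2022 analysis "reported results from the full model without any variable selection process, and with the data at Visit 3/Day 1 excluded". Sections 16.2.2.2 to 16.2.2.4 borrow the same procedure for the other endpoints and are also silent on Day 1.

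**The concern.** A row whose outcome is 0 by construction carries no information about treatment or variability. Entered as an outcome, it still counts as data. A structure that gives Day 1 its own variance can fit those rows perfectly, and the likelihood rewards this without limit. A structure with a single variance averages the zeros in.

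The affected outputs are the LS mean differences, CIs and p-values at Days 150 and 360. SAP v2.0 section 4.3 presents the Day 360 data as sufficient to judge efficacy and safety and as input to development milestones, so interval coverage matters even though the p-values are nominal.

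**Working it through.** The documents state no figure on this point, so there is none to reproduce first.

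**1. The value at Day 1.** Baseline is the last non-missing pre-dose measurement (SAP v2.0, 6.2). The first MMTT is on Day 1, with none at screening (Amendment 3 protocol, 8.3.1 and Table 3). The Day 1 C-peptide change is therefore 0 for every subject. For HbA1c, insulin and antibodies it is 0 wherever a Day 1 pre-dose value exists.

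**2. Which models use it.**

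| C-peptide model in 16.2.2.1 | Day 1 rows |
|---|---|
| Main | not stated |
| Exploratory, Day 150 lock, selection | included |
| Exploratory, Day 150 lock, selection | excluded |
| Exploratory, Day 360 lock, selection | excluded |
| Exploratory, Day 360 lock, full model | excluded |

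If the main model excluded Day 1, the first Day 360 exploratory model would duplicate it. Together with the Summary of Change, this makes inclusion the likelier reading. It remains an inference.

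**3. Structures with a separate Day 1 variance (UN, heterogeneous Toeplitz, heterogeneous AR(1)).** With the Day 1 means and all covariate slopes at 0, Day 1 is fitted exactly. The REML log-likelihood then rises by (n − p) × ln 10 for each tenfold fall in the Day 1 SD, where p is the number of mean parameters acting at Day 1. Seven covariates plus intercept and treatment give p = 9.

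- n = 24: (24 − 9) × 2.303 = 34.5 per step. Evaluated under UN at Day 1 SD 1, 0.1, 0.01, 0.001, 1e-4 and 1e-5: −35.5, −1.0, 33.5, 68.0, 102.6, 137.1.
- n = 21: (21 − 9) × 2.303 = 27.6 per step.
- Three covariates: (24 − 5) × 2.303 = 43.7. None: (24 − 2) × 2.303 = 50.7. Variable selection therefore does not rescue the fit.

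Because one slope serves all visits, the slopes are pulled to 0: the baseline coefficient went from −0.21 to −4e-11. In one data set the SE moved from 0.39 to 0.52 between optimiser restarts.

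**4. Homogeneous Toeplitz and AR(1).** These have a finite optimum, but the pooled variance includes the zeros. With T visits including Day 1 and equal post-baseline variances, the SE ratio is about √((T − 1)/T): √(2/3) = 0.82 for T = 3, √(4/5) = 0.89 for T = 5, √(6/7) = 0.93 for T = 7.

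**5. Simulation under no effect.** The documents give no SDs or correlations. Assumed: 16:8, residual correlation 0.7 (also 0.5 in the runs with later rows), baseline slope 0 to −1 residual SD per baseline SD, and, for rows at Days 1/150/360, Day 360 variance 1 to 2 times that at Day 150. Selection removes p ≥ 0.10 (the SAP gives no threshold). Entries are SE divided by true SD, then rejection at nominal 5%. Monte Carlo error at a 5% rate is about 1 to 1.5 points.

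| Rows and structure | Day 360 | Day 150 |
|---|---|---|
| Days 1/150/360, Toeplitz, seven covariates | 0.79–0.83; 9–12% | 0.84–1.05; 5–8% |
| Same, with selection | 0.76–0.81; 12–13% | 0.82–0.99; 5–11% |
| Same rows, Toeplitz, three covariates | 0.74–0.84; 9–12% | – |
| Same rows, AR(1), three covariates | 0.81–0.85; 10–11% | 0.84–1.05; 5–12% |
| Plus partial Day 540/720 rows, Toeplitz, converged fits | 0.87–0.98; 4–9% | 0.84–1.07; 2–12% |
| Plus partial Day 540/720 rows, AR(1) | 0.80–0.89; 7–11% | 0.78–1.03; 4–12% |

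In the fifth row, 12–28% of fits did not converge. A separate Toeplitz set on Days 1/150/360 (correlation 0.3 to 0.8, Day 360/Day 150 SD ratio 1.0 to 1.3) gave 0.72–0.83 and 10.3–15.3% at Day 360, the lowest ratios without covariates. Kenward-Roger does not repair this: median df were 43–52 with Day 1 in and 18–22 without.

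**6. Day 1 excluded, UN.** Full seven-covariate model: 0.98–1.04 and 3–5%. With selection: 0.90–0.96 and 6–8%. The separate set, without selection: 0.95–1.01 and 4.2–7.2%.

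**The case against.** The strongest reply concerns reach. The only text that places Day 1 rows in a model is one exploratory bullet. A reader might infer that the main models in 16.2.2.1 to 16.2.2.4 certainly include them; no sentence says so, and the change scores also feed by-visit summaries. This stands, and leaves the row set of the main models unstated.

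Second, size. A reader might take a two-row case, Day 1 and Day 150 only, as the expected behaviour of the Day 150 model that includes Day 1; simulation of that case gave 13–17% rejection. The documents do not support it. SAP v2.0 section 4 says all available data are analysed at the primary analysis. The first six subjects were at least a month past first dose before Amendment 3 of 01Feb2021 (protocol 4.7 and 5.6; SAP v2.0 section 1), so they were due at Day 360 by about the turn of 2021/22, before the 29APR2022 lock. How many later rows existed is not stated, so I put no single size on that model. By the same dating, Day 540 rows probably exist at the Day 360 lock, which favours the milder rows of the table.

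Third, which branch occurs depends on the software's convergence rule, which was not modelled. SEs that are too small arise only in the homogeneous fallbacks.

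Fourth, baseline can legitimately be an outcome in a longitudinal model. That is so for raw values without baseline as a covariate. Here the outcome is the change and baseline is also a covariate.

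Finally, the endpoints are secondary, p-values are nominal (7.4) and there is no primary efficacy endpoint (16.1). That limits the consequence but does not make the CIs right.

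**Conclusion.** The point holds and should be fixed. That the Day 1 C-peptide change is 0, and that UN and both heterogeneous structures then have no finite optimum, follows from the definitions and needs no assumed SDs. It applies for certain to one exploratory Day 150 model and probably, by inference, to the main models.

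The outcome is one of two. Either the software accepts a degenerate fit, the covariate adjustment is lost and the result depends on where the optimiser stops; or the fit ends at a homogeneous structure with a diluted variance. In the second case, with rows at Days 1/150/360, the Day 360 SE is roughly 0.74 to 0.85 of the true SD, with about 9 to 13% rejection; the separate set reached 0.72 and 15.3%. With Day 540/720 rows, or higher later variances as regards Day 150, the shortfall is smaller or absent. These sizes rest on assumed variances and correlations; dropout and treatment-affected covariates were not modelled. Confidence in the size is moderate.

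A reader might also infer that the June 2022 Day 150 result is compromised. It is not: section 16.2.2.1 says that analysis excluded Day 1.

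**What to change.** In SAP v2.0 sections 16.2.2.1 to 16.2.2.4, state that only post-baseline visits enter the MMRM as outcomes, with the baseline value kept as a covariate, in line with the SAP v1.0 definition and the June 2022 analysis. Use the Day 1 zeros in descriptive tables only. Label any fit that includes Day 1 as exploratory, with a note that its SEs may be unreliable. State which follow-up visits' rows are used at the Day 360 lock.

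For C-peptide AUC, report both Day 360 models without Day 1 that are already listed, with selection and full. Which of them should lead is a separate question.

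The cost is a SAP amendment, documented as made after unblinding (17MAY2022), and refitting of any model that used Day 1. No new data are needed. Nominal p-values may move either way. With selection in both, median simulated SEs with Day 1 in versus out were 0.35 v 0.42 at both visits (slope 0, equal variances). At slope −1 and variance ratio 2 they were 0.48 v 0.43 at Day 150 and 0.48 v 0.60 at Day 360.

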#### **16.2.1.2. Change from Baseline in HbA1c**

HbA1c will be measured at the first screening visit and at each dosing and long-term follow-up visit as per the schedule of events (refer to protocol Table 3).

Change from baseline in HbA1c will be computed for baseline and for each post-baseline visit.

#### **16.2.1.3. Change from Baseline in Total Daily Insulin Dose, Total Daily Basal Insulin Dose, and Total Daily Bolus Insulin Dose**

Total daily insulin will be entered by subjects on an insulin log for 3-7 days prior to each study visit starting with Study Day 1. Change from baseline in total daily insulin dose, total daily basal insulin dose, and total daily bolus insulin dose will be computed for baseline and for each post-baseline visit.

Because insulin is heavily dependent on weight at the same visit, the following measures will also be computed for baseline and for each post-baseline visit: change from baseline in total daily insulin dose divided by weight, total daily basal insulin dose divided by weight, and total daily bolus insulin dose divided by weight. This additional summary is included per the 22Apr2022 memo-to-file to amend the SAP v1.0.

#### **16.2.1.4. Change from Baseline in Autoantibody Levels**

Antibody levels to glutamic acid decarboxylase (GAD65), insulinoma associated protein (IA-2), zinc transporter 8 (ZnT8), and insulin associated aAb (IAA) will be measured at the first screening visit and at each dosing and long-term follow-up visit as per the schedule of event (refer to Protocol Table 3).

Change from baseline for each antibody type will be computed for baseline and for each post-baseline visit.

### **16.2.2. ANALYSIS OF SECONDARY EFFICACY ENDPOINTS**

Observed value and change from baseline for C-peptide AUC, HbA1c, total daily insulin dose, total daily basal insulin dose, total daily bolus insulin dose, and each of 4 antibodies will be summarized by treatment group and visit.

#### **16.2.2.1. Continuous Secondary Efficacy Endpoints – C peptide AUC**

For the primary analysis of C-peptide AUC, a Mixed-effect Model for Repeated Measurements (MMRM) will be performed based on the PD analysis population using the observed-case data. This model will include the change

Author:	[name]	Version Number:	2.0
		Version Date:	23Nov2022
Template No.:	CS_TP_BS016 Revision 6	Reference:	CS_WI_BS005
Effective Date:	02Dec2019		

from baseline variable as the dependent variable, its baseline observed value, age, and time from diagnosis to the first dose as covariates, treatment group (active and placebo), visit, HbA1c, BMI, total daily insulin divided by weight, potency assay, and treatment group-by-visit interaction as fixed effects. The fixed effects and covariates specified in SAP v1.0 were revised per the 22APR2022 memo-to-file to amend the SAP v1.0.

A backward stepwise variable selection process will be used to remove any non-relevant or highly correlated variables before fitting the final model. Restricted Maximum Likelihood (ReML) estimation will be used. An unstructured (UN) covariance structure will be used to model the within-patient error and an adjustment to the degrees of freedom will be made using the Kenward-Roger's approximation. In the event this model does not converge, the heterogeneous Toeplitz, heterogeneous first-order autoregressive (AR(1)), Toeplitz, and AR(1) covariance structures will be tested one after the other in the order listed here i.e., the heterogeneous Toeplitz covariance structure will be tested first and if this model converges, the other covariance structures will not be tested. If this model does not converge, then the heterogeneous AR(1) will then be tested. The same process will be repeated for each covariance structure one after the other as listed above until the model converges.

The Least Square (LS) mean estimates will be provided for each treatment group for each visit along with their standard error (SE). The difference of LS means between the treatment groups (active vs. placebo) and associated SE, two-sided 95% CI for each visit, and *p-value* will also be provided only for Visits at Day 150 and Day 360.

In addition, the following MMRMs for C-peptide AUC will be analyzed as exploratory analyses:

- MMRM, based on the data locked for the primary analysis when the last subject completes the Month 5 study visit (Day 150), with the data at Visit 3/Day 1 included. A separate backward stepwise variable selection process will be performed.
- MMRM, based on the data locked for the primary analysis when the last subject completes the Month 5 study visit (Day 150), with the data at Visit 3/Day 1 excluded. A separate backward stepwise variable selection process will be performed.
- MMRM, based on the data locked for the supplemental analysis when the last subject completes the Month 12 study visit (Day 360), with the data at Visit 3/Day 1 excluded. A separate backward stepwise variable selection process will be performed.
- MMRM, based on the data locked for the supplemental analysis when the last subject completes the Month 12 study visit (Day 360), with the data at Visit 3/Day 1 excluded. The full model will be fitted directly without any variable selection process. The primary analysis performed in June 2022 for Day 150 reported results from the full model without any variable selection process, and with the data at Visit 3/Day 1 excluded.

Author:	[name]	Version Number:	2.0
		Version Date:	23Nov2022
Template No.:	CS_TP_BS016 Revision 6	Reference:	CS_WI_BS005
Effective Date:	02Dec2019		

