## 7.6. ADJUSTMENTS FOR COVARIATES AND FACTORS TO BE INCLUDED IN ANALYSES

Mixed-effect Model for Repeated Measurements (MMRM) analyses C-peptide total AUC will be adjusted for treatment group, visit, HbA1c, BMI, total daily insulin divided by weight, potency assay, and treatment group-by-visit interaction as fixed effects. See section 16.2 for further details.

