#### 16.2.2.2. Continuous Secondary Efficacy Endpoints – HbA1C

For the analysis of HbA1C, a Mixed-effect Model for Repeated Measurements (MMRM) will be performed based on the PD analysis population using the observed-case data. This model will include the change from baseline variable as the dependent variable, its baseline observed value, age, and time from diagnosis to the first dose as covariates, treatment group (active and placebo), visit, C-peptide AUC, BMI, total daily insulin divided by weight, potency assay, and treatment group-by-visit interaction as fixed effects.

The MMRM modeling and selection procedures described in section 6.2.2.1 will be used to select an appropriate model for this endpoint.

The Least Square (LS) mean estimates will be provided for each treatment group for each visit along with their standard error (SE). The difference of LS means between the treatment groups (active vs. placebo) and associated SE, two-sided 95% CI for each visit, and *p-value* will also be provided only for Visits at Day 150 and Day 360.

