#### 16.2.2.3. Continuous Secondary Efficacy Endpoints – Total Daily Insulin Divided by Weight

For the analysis of total daily insulin divided by weight, a Mixed-effect Model for Repeated Measurements (MMRM) will be performed based on the PD analysis population using the observed-case data. This model will include the change from baseline variable as the dependent variable, its baseline observed value, age, and time from diagnosis to the first dose as covariates, treatment group (active and placebo), visit, C-peptide AUC, BMI, HbA1C, potency assay, and treatment group-by-visit interaction as fixed effects.

The MMRM modeling and selection procedures described in section 6.2.2.1 will be used to select an appropriate model for this endpoint.

The Least Square (LS) mean estimates will be provided for each treatment group for each visit along with their standard error (SE). The difference of LS means between the treatment groups (active vs. placebo) and associated SE, two-sided 95% CI for each visit, and *p-value* will also be provided only for Visits at Day 150 and Day 360.

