#### 16.2.2.4. Continuous Secondary Efficacy Endpoints – Antibody Levels to Glutamic Acid Decarboxylase (GAD65), Insulinoma Associated Protein (IA-2), Zinc Transporter 8 (ZnT8), and Insulin Associated aAb (IAA)

For the analysis of each of the antibody levels to glutamic acid decarboxylase (GAD65), insulinoma associated protein (IA-2), zinc transporter 8 (ZnT8), and insulin associated aAb (IAA), a Mixed-effect Model for Repeated Measurements (MMRM) will be performed based on the PD analysis population using the observed-case data. This

Author:	[name]	Version Number:	2.0
Template No.:	CS_TP_BS016 Revision 6	Version Date:	23Nov2022
Effective Date:	02Dec2019	Reference:	CS_WI_BS005

model will include the change from baseline variable as the dependent variable, its baseline observed value, age, and time from diagnosis to the first dose as covariates, treatment group (active and placebo), visit, C-peptide AUC, HbA1C, BMI, total daily insulin divided by weight, potency assay, and treatment group-by-visit interaction as fixed effects.

The MMRM modeling and selection procedures described in section 6.2.2.1 will be used to select an appropriate model for these endpoints.

The Least Square (LS) mean estimates will be provided for each treatment group for each visit along with their standard error (SE). The difference of LS means between the treatment groups (active vs. placebo) and associated SE, two-sided 95% CI for each visit, and *p-value* will also be provided only for Visits at Day 150 and Day 360.

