## ALGORITHM FOR POTENCY ASSAY

As specified in the inclusion criteria 3 in the protocol, a subject is eligible for enrollment as the study participant, only if the subject “has a CD8+ T cell defect that is correctable in vitro by co-culture with immature dendritic cells loaded with the synthetic oligopeptide from Hsp60sp”.

Therefore, for the potency assay result of each patient on Visit 3/Day 1 (before the study treatment), should be imputed as the same as the corresponding potency assay result on Visit 1/Screening.

For potency assay results that are missing on any visits other than Visit 3/Day 1, no imputation will be performed.

---

Author: [name]

Version Number: 2.0

Template No.: CS\_TP\_BS016 Revision 6

Version Date: 23Nov2022

Effective Date: 02Dec2019

Reference: CS\_WI\_BS005

---

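### The efficacy MMRMs give no time point for the potency, HbA1c, BMI, insulin and C-peptide covariates; where post-dose values enter, the contrast is not the total effect of AVT001

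*Combined protocol and SAP*

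**What the plan says.** **Model terms.** Section 7.6 of SAP v2.0 adjusts the C-peptide MMRM for "treatment group, visit, HbA1c, BMI, total daily insulin divided by weight, potency assay, and treatment group-by-visit interaction as fixed effects", and 16.2.2.1 repeats the list: "treatment group (active and placebo), visit, HbA1c, BMI, total daily insulin divided by weight, potency assay, and treatment group-by-visit interaction as fixed effects". The HbA1c model (16.2.2.2) has "visit, C-peptide AUC, BMI, total daily insulin divided by weight, potency assay, and treatment group-by-visit interaction as fixed effects". The insulin/weight model (16.2.2.3) has "visit, C-peptide AUC, BMI, HbA1C, potency assay, and treatment group-by-visit interaction as fixed effects". The four antibody models (16.2.2.4) have "visit, C-peptide AUC, HbA1C, BMI, total daily insulin divided by weight, potency assay, and treatment group-by-visit interaction as fixed effects". In all of them only the endpoint's own baseline value, age and time from diagnosis to first dose are clearly pre-dose. Section 6.2 defines baseline but does not apply it to the other terms. SAP v1.0 (7.6, 16.2.2.1) has the same gap for C-peptide; it planned only univariate summaries for the other secondary endpoints.

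**Potency.** Appendix 1 of v2.0 copies the Screening result into Day 1 and adds: "For potency assay results that are missing on any visits other than Visit 3/Day 1, no imputation will be performed". The Summary of Change notes that potency was never due on Day 1. It also says that change from baseline is now defined at baseline, so that Day 1 rows can enter the MMRM.

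**Output.** On Day 150, 16.2.2.1 records: "The primary analysis performed in June 2022 for Day 150 reported results from the full model without any variable selection process", with Day 1 rows excluded. For the other endpoints the plan promises: "The Least Square (LS) mean estimates will be provided for each treatment group for each visit along with their standard error (SE".

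**The concern.** A randomised contrast keeps its meaning as the total treatment effect when the model adjusts only for variables fixed before dosing. Potency is a secondary endpoint (SAP v2.0, 2.2) and measures the pathway through which AVT001 is meant to act (Protocol Amendment 3, 10.3). A model that holds post-dose potency equal between arms asks what AVT001 does apart from that pathway. Post-dose HbA1c, insulin or C-peptide raise the same difficulty.

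These MMRMs are the only planned efficacy analyses that give a between-arm difference with a confidence interval and p-value. SAP v2.0 section 4.3 intends the Day 360 results to inform development decisions. As written, two statisticians could fit different models, and a reader could not tell which effect had been estimated.

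**Working it through.** The plan states no figure on this point, so there is none to reproduce.

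**Step 1: which reading does the text support?**

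- *Potency: same-visit, at least in models with Day 1 rows.* Under 6.2 the Screening result already is the baseline value, so a baseline covariate needs no Day 1 imputation. A row-by-row covariate does. For models that exclude Day 1, including the June 2022 full model, the inference is only indirect, and v1.0 (7.2) had no such rule.
- *BMI: leans to baseline.* Sections 10, 10.1, 12 and 12.1 derive it at diagnosis, screening and baseline. Section 17.4 lists weight at later visits, but neither height nor BMI.
- *C-peptide AUC as covariate: unsettled, but baseline fits better.* Same-visit AUC could not supply the per-visit LS means promised in 16.2.2.2 to 16.2.2.4 (Step 2).
- *HbA1c and insulin/weight: unsettled.* Table 3 schedules both on Day 1 and at every later visit, so the schedule does not discriminate.

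**Step 2: usable visits through Day 360** (protocol Table 3)

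- HbA1c, insulin, antibodies: Days 30, 60, 90, 150, 270, 360 (six).
- Potency: Days 90, 150, 270, 360 (four).
- MMTT: Days 150, 360 (two).

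In an observed-case fit of the full models for HbA1c, insulin and antibodies, with 24 subjects:

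| Reading | Visits kept | Planned records |
|---|---|---|
| Potency and AUC both baseline | 6 of 6 | 24 × 6 = 144 |
| Only potency same-visit | 4 of 6 | 24 × 4 = 96 |
| AUC same-visit | 2 of 6 | 24 × 2 = 48 |

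The C-peptide model keeps all its visits, and Days 150 and 360 survive every reading.

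**Step 3: size under same-visit potency (illustration)**

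In a linear model at one visit, adjusted contrast = T − Δ × β. T is the total effect, Δ the arm difference in potency, and β the within-arm slope of outcome on potency. If a share s of the effect runs through potency and nothing else links the two, then β = sT/Δ and the contrast is (1 − s)T.

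Assumed: T = 1 residual SD and 16:8 allocation. The single-visit simulation has a 1 SD potency shift and 20,000 runs. The two-visit MMRM (unstructured, REML) has potency reversal of 60% against 0%, taken from the superseded original protocol (6.1), within-subject correlation 0.6, and 600 trials per cell (Monte Carlo error about 0.02).

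| s | (1 − s)T | Single visit: same-visit potency | Single visit: pre-dose only | MMRM Day 360: same-visit potency | MMRM Day 360: pre-dose only |
|---|---|---|---|---|---|
| 0% | 1.00 | 1.00 | 1.01 | 0.98 | 0.97 |
| 25% | 0.75 | 0.76 | 1.01 | 0.74 | 0.98 |
| 50% | 0.50 | 0.49 | 0.99 | 0.51 | 1.01 |
| 75% | 0.25 | 0.25 | 1.00 | 0.27 | 1.03 |
| 100% | 0.00 | 0.00 | 1.00 | 0.02 | 0.99 |

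At s = 50% the single-visit power is 16% with same-visit potency and 46% with pre-dose covariates. If potency enters at its Screening value, nothing is lost.

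**Step 4: direction**

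With no mediation, a 1.5 SD potency shift and a shared cause giving a within-arm slope of +0.25 or −0.25, the formula gives 1 − 1.5 × 0.25 = 0.625 or 1 + 1.5 × 0.25 = 1.375. Simulation gave 0.63 and 1.38. With a true effect of zero, a potency shift of 1, within-arm potency variance 1.25 and shared covariance 0.3 or 0.5, the bias is −0.3/1.25 = −0.24 or −0.5/1.25 = −0.40. Simulation gave −0.24 and −0.40, with rejection in 7.6% and 13.9% of runs instead of 5%.

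**The case against.** The plan may be sound in operation. The memo-to-file that revised the C-peptide covariates, and the TFL shells, could state the timing. If all terms are baseline values, every MMRM already uses pre-dose covariates. This stands, and it limits the claim: no MMRM is *explicitly* restricted to pre-dose covariates. A reader might go further and infer that the SAP adjusts for post-dose variables throughout, or that the June 2022 Day 150 result is biased. The documents do not support that. The evidence for same-visit values concerns potency only and is indirect for models without Day 1 rows.

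Protocol Amendment 3 calls these effects exploratory (5.7) and describes the MMRM as a means of presenting data (9.8). There is no primary efficacy endpoint, and p-values are nominal. By-arm means and SDs are planned, so a reader could derive an unadjusted difference. All of this bears on severity. It does not remove the need to say which effect the reported contrast and p-value estimate.

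Backward selection might drop potency. With a 0.05 threshold (assumed; none is stated), a single-visit simulation gave 1.00, 0.92, 0.75, 0.44 and 0.10 SD at the five mediated shares: less shrinkage, but dependent on the data. The June 2022 model used no selection.

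The simulated sizes rest on assumed effects and mediated shares, and only potency was simulated. The SD is a residual one, so standardised effect and power are not strictly comparable across rows. The figures show a mechanism and do not measure a bias in this trial.

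**Conclusion.** The point holds as a gap that should be fixed. The SAP leaves covariate timing open in all seven efficacy models. For potency, the covariate for which timing matters most, its own imputation rule leans towards post-dose values. To the extent that post-dose values are used, the Day 150 and Day 360 contrasts do not estimate the total effect of AVT001. In the illustration the estimate falls from 1 SD towards zero as the mediated share rises, and a shared cause can move it up or down. The true size cannot be given from these documents. The safety objective is untouched. Confidence is medium, because two documents that could settle the timing were not available.

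**What to change.** Use the SAP amendment that v2.0 section 4.4 already foresees before the final lock.

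1. State for every covariate in 7.6 and 16.2.2.1 to 16.2.2.4 whether it is the baseline or the same-visit value.
2. For each endpoint, specify one MMRM without variable selection, with treatment, visit, treatment-by-visit and a fixed list of pre-dose covariates: the endpoint's baseline value, age and time from diagnosis. If further terms are used, take the baseline values of that endpoint's listed covariates, including Screening potency and, outside the C-peptide model, baseline C-peptide AUC. Fix that choice in the amendment, not from the data. Report this model as the total-effect estimate, labelled as added after the 17 May 2022 unblinding, next to the models already specified. If item 1 confirms that all terms are baseline values, the existing full C-peptide model without selection already serves for C-peptide.
3. Label any model with post-dose covariates as mechanistic.

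The cost is one amendment and up to 1 + 1 + 1 + 4 = 7 extra models (C-peptide AUC, HbA1c, insulin/weight, four antibodies), with no new data. The downside is that they come after unblinding and must be disclosed as such. The C-peptide covariate list was set before unblinding and should stay in the report. The lists for the other endpoints first appear in v2.0, after unblinding.
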